9.1.9 Randomization

The timing of randomization will follow shortly after baseline assessments and final confirmation of eligibility. Participants will be encouraged to initiate treatment within 28 days of randomization. If a participant is unable to initiate treatment within 28 days, he or she may initiate XR-NTX study drug at any time until week 20 and may initiate TAU at any time during the trial. Initiation of assigned treatment will be tracked.

Participants will be randomized in a 1:1 fashion to either office-based XR-NTX or TAU using a permuted block design with randomly-sized blocks. Randomization will be stratified only by site. Participants who meet DSM-5 criteria for both opioid and alcohol use disorder (16% of CTN-0055 CHOICES pilot study participants) will be included, in addition to participants with OUD, alone.

Concomitant alcohol use disorder will be considered as a potential covariate [31], [127, 128]. Participants need not be abstinent from opioids at the time of randomization.

The randomization procedure will be conducted in a centralized process through the Data and Statistics Center (DSC). Specifically, randomization schedules will be created by the study statistician for each site. The randomization schedules will be of a randomized-block nature to ensure relative equality of assignment across condition across the recruitment period and to prevent the potential for study staff guessing the next assignment, which is heightened when a fixed block-size is used. After the baseline assessment is successfully completed, a designated site study staff member will perform the randomization. Randomization for each participant is done over the internet using the Enrollment Module in Advantage eClinical.

The DSC statistician will review the randomization data on a regular basis to ensure that the scheme is being implemented according to plan. If a participant drops out of the study at any point after randomization, the randomization slot will not be re-allocated to a new participant due to the intent-to-treat nature of the study.

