Among the 9 individuals in the pilot study who had opioid use disorder and were unsuppressed at baseline, 6 (17%) of the 36 subsequent viral load values were missing. In the pilot, viral load was measured monthly, increasing the opportunity for missing data, whereas CTN-0067 collects follow-up viral loads only at 12 and 24 weeks and will likely have fewer missing viral loads. The primary outcome analysis will be carried out using the binary repeated measures of viral load (RMVL) framework of Rose et al., a type of time series model. In theory, time series models can accommodate missing data better than non-longitudinal models by using all non-missing data points. However, this approach assumes that missing data are not informative, that is, that missing values are probably similar to corresponding non-missing values with the same set of other predictors. For substance-use trials, missing at random (MAR) is less likely than missing not at random (MNAR) alternative: if data are missing, it is probably because the participant is unsuppressed. So, for the primary analysis, “unsuppressed” will be substituted for missing suppression status values. Since death is at least as undesirable as lack of suppression, “unsuppressed” will be assigned as a status value for visits subsequent to death. A secondary sensitivity analysis will explore the extent to which trial conclusions need to be changed as the missingness assumption approaches MAR.

9.2.3.4 *Dispensing of XR-NTX*

Study medication (XR-NTX) will be provided by the study at no cost to the participant. XR-NTX will be administered in clinic at the Treatment Initiation Visit and at treatment weeks 4, 8, 12, 16 and 20.

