17.0 STATISTICAL ANALYSIS

17.1 Primary Objective of the Analysis

The Primary objective of the CTN-0067 CHOICES scale-up study is to discover whether HIV clinic-based XR-NTX is non-inferior to TAU with respect to HIV viral suppression in HIV-infected participants with opioid use disorder. We have chosen a non-inferiority margin of 0.75. That is, we will reject the null hypothesis of inferiority of XR-NTX to TAU in favor of non-inferiority if the lower 95% confidence limit for the ratio $\frac{\text{Pr}(\text{suppressed}|\text{NTX})}{\text{Pr}(\text{suppressed}|\text{TAU})}$ is strictly greater than 0.75. We anticipate a sample size of 350 (175/arm) will grant at least 80% power for the non-inferiority conclusion.

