- a. **Days of Opioid Use** Number of days of opioid use between baseline and 24 weeks, measured by TLFB (count; self-report), will be used to compare opioid use by treatment group. Confirmatory analysis will assess opioid use by the number of days of opioid use in the last 30 days of the study (by ASI-lite; count; self-report) and the number of monthly urine drug screen (UDS) negative for opioids between baseline and 24 weeks (count; laboratory data). *Analyzed using rank-based methods such as Wilcoxon rank-sum tests.*
- b. **Opioid Abstinence** Past 30 day opioid abstinence (by Addiction Severity Index (ASI)-lite self-report, Time-Line Follow-Back (TLFB) and urine drug screen (UDS) confirmation) in the final 30 days of the 24 week trial (binary; self-report + UDS).

Analyzed via rank-based methods such as Wilcoxon rank-sum tests. Covariates can be considered via the cumulative logit model.

Mediation Analysis

Mediation will be tested using structural equation modeling with Mplus 7.3. These models estimate the effect of the intervention on the potential mediator (path a, e.g., the effect of intervention on *substance use*) and the effect of the mediator on the outcome or next proximal intermediate outcome (path b, e.g., the effect of *substance use* on *HIV medication adherence*). Longer mediation pathways can also be tested (e.g., a^*b^*c), and therefore the entire mediational path depicted in section 1.2.1 can be assessed in this framework. There is significant mediation if the product of these two paths (a^*b) is greater than zero (or the product of more pathways in a longer mediational chain). Statistical significance will be assessed using bias-corrected bootstrap confidence intervals on the product terms [171]. This test is by far the most powerful test of mediation [172] and can test multiple mediating pathways within a single structural model. Using the tables in Fritz and MacKinnon [171], we should have over 80% power for mediation when the standardized path coefficients (a and b) are .164, which corresponds to approximately 2.7% shared variance between the outcome and predictor variable (e.g., treatment and substance for the a-path in the example given above.) We will also examine whether there are differences in strength of mediational pathways across the opioid and alcohol disorder subgroups.

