17.9.1 Additional Statistical Tests of the Secondary Outcomes

In addition to the methods described after each secondary outcome, statistical modeling will be done using generalized estimating equations (GEEs) models as employed by Liang and Zeger [174] to allow covariate adjustment in factors such as concomitant alcohol use disorder and severity of opioid and alcohol use disorder. Those secondary outcomes that are binary will be tested with a binomial distribution and logit link as implemented in SAS; whereas those secondary outcomes that involve either continuous or ordinal variables will utilize the appropriate distribution and link function. Note that the exact method of analysis will depend on the realized distribution of the particular outcome in this trial. For example, an expected count data variable may need to be modeled using a zero-inflated Poisson regression rather than a standard Poisson regression if there are too many zero observations to fit the standard Poisson. If there is over-dispersion, a

negative binomial (or zero-inflated negative binomial) regression may be appropriate. For these secondary analyses, the overall Type I error will not be controlled.

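### The bias-corrected bootstrap chosen for mediation runs at about 7% rather than 5% when one path is .164 and the other is zero, and its power advantage comes from that excess

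*Combined protocol and SAP*

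**What the plan says.** The Mediation Analysis part of Section 17.9 fits structural equation models. Path a runs from treatment to the mediator (for example substance use) and path b from the mediator to the outcome (for example HIV medication adherence). Mediation is judged on the product of the paths: "Statistical significance will be assessed using bias-corrected bootstrap confidence intervals on the product terms".

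Two reasons are given. The main one is power: "This test is by far the most powerful test of mediation". The other is that several pathways can be tested in one model. The power statement is that "we should have over 80% power for mediation when the standardized path coefficients (a and b) are .164", glossed as a path size "which corresponds to approximately 2.7% shared variance between the outcome and predictor variable".

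The section gives no interval level, no number analysed for mediation, no false-positive rate for the method, and no alternative or check. Section 17.9.1 adds, for the secondary outcomes generally: "For these secondary analyses, the overall Type I error will not be controlled".

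**The concern.** The bias-corrected (BC) interval moves both percentile limits according to where the estimate sits in its bootstrap distribution. A product of two path estimates has a skewed distribution, with the long tail pointing away from zero. The estimate therefore tends to lie beyond the bootstrap median, and the correction pushes both limits further from zero. When one path is real and the other is zero, the product is truly zero, and this shift can make the interval exclude zero too often.

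That null is realistic here. The conceptual model in Section 4.1 has opioid use acting on ART adherence, so path b is plausibly non-zero. The comparator is usual care linked to agonist treatment (Section 9.2.4), and the design alternative is no difference between arms in suppression (RR = 1, Section 17.12). A treatment effect on opioid use close to zero is therefore a live possibility. A liberal test could then credit XR-NTX with an effect on adherence through opioid use that it does not have. The plan's main reason for choosing the method would also be partly a product of its liberality.

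**Working it through.** **Inputs**
- Test, and path size a = b = .164: Section 17.9. Check: .164² = .0269, which agrees with the stated 2.7%.
- Sample size 350: "We anticipate a sample size of 350 (175/arm) will grant at least 80% power for the non-inferiority conclusion" (Section 17.1). No separate number is given for mediation, so the full sample is assumed.
- Allocation: "Participants will be randomized in a 1:1 fashion to either office-based XR-NTX or TAU" (Section 9.1.9).
- Two-sided 5% level (95% interval): assumed.
- Model: M = aX + error and Y = bM + error, with standardized paths and Y regressed on M and X: assumed.

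**Tests compared**
- BC bootstrap: limits for the product at bootstrap quantiles Φ(2z₀ ± 1.96), where z₀ = Φ⁻¹(share of bootstrap products below the estimate).
- Percentile bootstrap: limits at the 2.5% and 97.5% quantiles.
- Joint significance: both paths significant at two-sided 5%.

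Each cell has 8,000 simulated trials with 1,000 resamples each.

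**Step 1: reproduce the plan's figure.** At a = b = .164 and N = 350, BC power is 81.6%, which agrees with the plan. The percentile interval gives 73.4% and joint significance 74.5%. As an analytic check on the last:
- Path a: Φ(.164·√350/√(1 − .164²) − 1.96) = Φ(1.15) = .875
- Path b, given treatment: Φ(.164·√350 − 1.96) = Φ(1.11) = .866
- Product: .875 × .866 = .758, close to the simulated value.

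**Step 2: rejection of a true null at N = 350**

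| a | b | BC | Percentile | Joint |
|---|---|---|---|---|
| .164 | 0 | 7.3% | 4.2% | 4.2% |
| 0 | .164 | 7.2% | 3.8% | 4.1% |
| .25 | 0 | 7.2% | 5.2% | 4.9% |
| 0 | .25 | 6.9% | 5.0% | 4.6% |
| .40 | 0 | 5.9% | 5.2% | 4.7% |
| 0 | .40 | 5.8% | 5.2% | 4.9% |
| 0 | 0 | 0.8% | 0.2% | 0.4% |

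The Monte Carlo standard error at 7.3% is √(.073 × .927/8000) = 0.3 points, so an excess of 2.3 points over 5% is not noise. A normally distributed X in place of the treatment indicator gives BC 7.3% and 7.8% in the first two rows.

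**Step 3: coverage and width**
- One path .164, the other zero: BC covers 92.7% and 92.8%. Mean width in the first of these cells is 0.040, against 0.039 for the percentile interval.
- Both paths .164: BC covers 95.9%. Mean width is 0.052, against 0.050.

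The BC intervals are slightly wider than the percentile intervals. The under-coverage comes from where they are placed.

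**Step 4: power at equal size.** A further run used 24,000 trials pooled over the two .164 one-path nulls and 12,000 at a = b = .164. It found the nominal level at which each test has a true 5% size.

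| Test | Size at nominal 5% | Power at nominal 5% | Nominal level for 5% size | Power at 5% size |
|---|---|---|---|---|
| BC | 7.6% | 81.6% | 3.4% | 75.9% |
| Percentile | 4.0% | 73.3% | 5.8% | 76.4% |
| Joint | 4.5% | 75.3% | 5.5% | 76.6% |

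**Step 5: departures from the ideal setting.** Section 9.2.3 reports that in a pilot subgroup "6 (17%) of the 36 subsequent viral load values were missing". Applying that rate to the mediation data, as an assumption, leaves 350 × (1 − .17) ≈ 290. At N = 290, power at .164 is 71% (BC), 61% (percentile) and 63% (joint), and BC one-path null rejection is 7.0-7.3%. With a binary outcome split at 50%, N = 350 and linear models, power is 68%, 58% and 59%, and BC null rejection (a = .164, b = 0) is 7.3%.

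**The case against.** Much can be said for the plan. Its power figure is not an arithmetic error: it is right for the test named. At the stated design point, with both paths at .164, mediation is real and BC coverage is sound. The percentile interval is not exact either: at the .164 nulls the choice is between about 2 points liberal and about 1 point conservative. The analysis is secondary and mechanistic, and no confirmatory claim rests on it. All of this stands.

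The Type I statement in Section 17.9.1 does not answer the point. It concerns the error rate over many analyses, not whether one test reported at 5% holds 5%.

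The interval level is assumed. Section 17.9 also describes mediation as a product above zero. Read as one-sided, about half of the rejections would count against a 2.5% benchmark, which leaves the relative excess the same.

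Three stronger readings are tempting and not supported:
- That the intervals are too narrow. They are slightly wider on average; they are shifted.
- That the test rejects any true null at 7%. With both paths zero it rejects under 1%, and the excess shrinks as the non-zero path grows.
- That part of the stated power consists of false positives. When both paths are non-zero, a rejection in the right direction is correct. The advantage arises because the test runs above its nominal level.

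**Conclusion.** The concern holds in a limited form. With one path at .164 and the other at zero, the BC test rejects at about 7% against a nominal 5%, with coverage of about 93%. The alternatives reject at about 4%. The BC power advantage of about 7 to 8 points (82% against 73-75%) is gone once the tests have equal size. The plan's main reason for preferring the method therefore does not hold up.

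This rests on a two-sided 5% level, 350 analysable participants and a linear single-mediator model with continuous variables, none of which the plan states for mediation. The excess null rejection persisted at N = 290 and with a binary outcome, but power did not. Section 17.3 defines adherence as binary and restricts it to those prescribed ART, so even 73-75% is optimistic for that outcome. The primary non-inferiority conclusion is not affected.

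**What to change.** In the Mediation Analysis part of Section 17.9:
1. State the interval level and whether the test is two-sided.
2. Test the product with the percentile bootstrap or the joint-significance test. If BC is kept, prespecify one of these as a check on any BC-significant result. The percentile interval uses the same resamples, so several pathways can still be tested in one model.
3. Restate power at paths of .164 as about 73-75%, labelled as assuming continuous mediator and outcome and all 350 analysable. Add that it is lower for the binary adherence outcome in those prescribed ART, and with missing data.
4. Remove the claim that the method is the most powerful, or qualify it with the false-positive rate.

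The cost is a short text edit, a change of interval option, and a lower stated power for a secondary analysis. Data collection and trial conduct do not change.

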17.9.1 Additional Statistical Tests of the Secondary Outcomes

In addition to the methods described after each secondary outcome, statistical modeling will be done using generalized estimating equations (GEEs) models as employed by Liang and Zeger [174] to allow covariate adjustment in factors such as concomitant alcohol use disorder and severity of opioid and alcohol use disorder. Those secondary outcomes that are binary will be tested with a binomial distribution and logit link as implemented in SAS; whereas those secondary outcomes that involve either continuous or ordinal variables will utilize the appropriate distribution and link function. Note that the exact method of analysis will depend on the realized distribution of the particular outcome in this trial. For example, an expected count data variable may need to be modeled using a zero-inflated Poisson regression rather than a standard Poisson regression if there are too many zero observations to fit the standard Poisson. If there is over-dispersion, a

negative binomial (or zero-inflated negative binomial) regression may be appropriate. For these secondary analyses, the overall Type I error will not be controlled.

17.10 ITT and Per-Protocol Analyses, Missing Data and Dropouts

Analysis will be ITT in the sense that participants will be analyzed as being members of the arm to which they were originally randomized. With one exception, we plan in the primary analysis to recode missing data to “unsuppressed” because, in this setting, this seems more realistic than assuming that missingness is non-informative for suppression. The exception is that, if missing data are flanked on both sides by “suppressed” values, we will impute the missing data to be suppressed. Sensitivity analyses will secondarily explore the implications of this MNAR imputation, and outcomes according to treatment received. Per-protocol sensitivity analyses will compare outcomes among those who initiated at least one dose of XR-NTX compared with those who initiated at least one dose of buprenorphine or methadone.

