9.1.7 Collection of Biological Specimens

Study staff will collect blood specimens at screening, randomization, 12 weeks, and 24 weeks to confirm eligibility and assess the primary outcome of HIV-1 RNA PCR and secondary outcomes of CD4 count, VACS Index, and hepatotoxicity. CBC, serum creatinine, LFTs (AST, ALT), INR, and HIV-1 RNA blood specimens will be collected during screening. CD4, Hepatitis C, Hepatitis B, and PBMC specimens will be collected and processed only after the participant has been randomized. Study staff will collect urine specimens during screening and at treatment initiation (XR-NTX arm only), safety visit (XR-NTX arm only), and at 4, 8, 12, 16, 20, and 24 weeks to confirm eligibility and assess secondary outcomes and pregnancy. Screening and randomization labs (CD4, HIV-1 RNA, and hepatitis B and C serologies) drawn in the 90 days prior to date of informed consent may be abstracted from participant medical records, when available. Other screening lab tests may be abstracted from medical records if drawn within 30 days prior to the date of informed consent, with the exception of urine specimens, which must be collected by study personnel. Some participating sites may require that copies of some or all lab results collected for study purposes be filed in participants' medical records.

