9.2.2 Medical Management (when applicable)

Study clinicians will be trained in medical management (MM). MM is a brief counseling intervention delivered by non-addiction medical providers to improve response to medication-assisted addiction treatments delivered in medical settings [129] [130]. It has augmented care for medication-assisted treatment of alcohol dependence with acamprosate and oral naltrexone in the COMBINE study [131], integration of XR-NTX treatment of alcohol dependence in primary care settings [36], and integration of BUP/NX for treatment of opioid dependence in primary care [132]. Since MM is meant to facilitate medication-assisted addiction treatment, it will be performed only for participants offered medication-assisted treatment in the HIV clinic (e.g., participants with opioid use disorders randomized to XR-NTX and TAU participants receiving clinic-based buprenorphine/naloxone or methadone for opioid use disorder). TAU participants referred for off-site methadone maintenance or buprenorphine/naloxone will not receive MM since medical

oversight is the responsibility of the treating provider. TAU participants who receive non-medication-assisted treatments such as 12-step groups or psychosocial counseling will not receive MM. During brief MM sessions, study clinicians will review recent drug and alcohol use, recommend abstinence, review medication side effects, and encourage adherence to medication-assisted treatment and participation in clinic and/or community support groups.

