The RMVL is a type of longitudinal model. In theory, longitudinal models can accommodate missing data better than non-longitudinal models because they incorporate all non-missing data points. But this approach assumes that missing data are not informative, that is, that missing values are probably similar to corresponding non-missing values with the same set of other predictors. For trials of substance-using individuals, missing at random (MAR) is less likely than missing not at random (MNAR) alternative: if data are missing, it is probably because the participant is unsuppressed. So, for the primary analysis, “unsuppressed” will be substituted for missing suppression status values. An exception is that, if missing data are flanked on both sides by “suppressed” values, we will impute the missing data to be suppressed. Since death is at least

as undesirable as lack of suppression, “unsuppressed” will be assigned as a status value for visits subsequent to death. A secondary sensitivity analysis will explore the extent to which trial conclusions need to be changed as the missingness assumption approaches MAR.

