17.7 Rationale for Sample Size

Figure 4 shows the non-inferiority margin required for power of (0.8, 0.9) (using the lower tail of the two-sided 95% confidence interval) as a function of the sample size for the non-inferiority test of XR-NTX versus TAU at 4 months, as estimated from data “random-assignment-bootstrapped” from the (opioid + overlap) group who were unsuppressed at baseline in the pilot study (CTN-0055). There are only 9 participants in the bootstrap population: 7 in Core and 2 in UBC. The random-assignment bootstrap approach was used at 4 months as a conservative way to estimate power in the scale-up (see appendix). The margin is expressed in terms of the risk ratio (RR), that

is, $\Pr(\text{suppressed} \mid \text{XR-NTX}) / \Pr(\text{suppressed} \mid \text{TAU})^1$. A horizontal reference line in **Figure 4** marks $\text{RR} = 0.75$, and vertical reference lines mark the intersection of the horizontal line with the power curves for $(0.8, 0.9)$. The vertical lines intersect the N axis at sample sizes of about $(350, 480)$. For a given sample size, use of a margin at or below the one specified by the relevant curved line will grant power in excess of that depicted by the line. For example, an RR margin less than or equal to 0.75 will grant a power of at least 90% for total sample size (both arms together) of about 480 , and will grant a power of at least 80% for total sample size of 350 . We have chosen this last point upon which to base our sample size.

This particular example is calculated using the Rose et al. binary RMVL model. The fixed effects in the model are treatment, visit number (continuous), time by treatment interaction, baseline alcohol, and site (categorical). The data for each participant are assumed to have an exchangeable correlation structure. Missing data are assumed to be unsuppressed. Note that cases in which the model failed to converge or converged but SAS flagged the result as questionable have been dropped from this analysis. The number of analyzed iterations was $(9020, 9492, 9696, 9819, 9848, 9869, \text{ and } 9911)$ for $n = (200, 250, 300, 350, 400, 450, 500)$, respectively. With the assumptions above, a non-inferiority sample size calculation was performed using commercial software PASS and got very similar results.

17.7.1 Figure 4. Non-inferiority margins granting power = 0.8 and 0.9 as a function of sample size

Additional Comments Concerning Choice of RR margin

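### Recoding missing viral loads to unsuppressed in both arms is not reliably conservative for non-inferiority, and the planned sensitivity analysis stops at MAR without being stated to vary by arm

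*Combined protocol and SAP*

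**What the plan says.** Section 17.1 sets the test: "We have chosen a non-inferiority margin of 0.75", as a risk ratio of XR-NTX to TAU. Non-inferiority is concluded if the lower 95% confidence limit exceeds that value.

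Section 17.10 describes an analysis by randomized arm in which "we plan in the primary analysis to recode missing data to" unsuppressed. The reason given is realism: in this population a missing value is thought more likely to be an unsuppressed one. The plan does not call the recode conservative. Sections 17.2 and 9.2.3.3 give the same rule, and visits after death also count as unsuppressed. Sections 17.2 and 17.10 make one exception, for a missing value with suppressed values on both sides.

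Section 17.2 describes the check: "A secondary sensitivity analysis will explore the extent to which trial conclusions need to be changed as the missingness assumption approaches MAR". Section 17.10 adds that sensitivity analyses will explore the implications of the imputation, and it plans analyses by treatment received and per protocol. Neither section gives a method, imputation values by arm, a tipping point, or a rule for results that disagree.

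The trial is unblinded (9.7). Contact differs somewhat by arm. Urine is collected at "treatment initiation (XR-NTX arm only), safety visit (XR-NTX arm only"), and 9.2.2 says "TAU participants referred for off-site methadone maintenance or buprenorphine/naloxone will not receive MM".

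**The concern.** In a superiority trial, counting missing as failure is often taken to be cautious. In a non-inferiority trial scored on a risk ratio, that depends on which arm has more missing values. The recode shrinks each arm's rate toward zero in proportion to its missing values. If TAU loses more, the comparator looks worse than it is and the ratio rises, so a difference in retention could produce or strengthen a non-inferiority finding.

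The second question is whether the planned sensitivity analysis would show this. A path from unsuppressed to MAR covers one kind of departure. It does not cover missing TAU participants doing well while missing XR-NTX participants do badly, which is the pattern most damaging to a non-inferiority claim.

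**Working it through.** **Inputs from the documents.** Margin 0.75 (17.1). "Participants will be randomized in a 1:1 fashion" (9.1.9). "We anticipate a sample size of 350 (175/arm) will grant at least 80% power for the non-inferiority conclusion" (17.1). One-sided 0.025, "using the lower tail of the two-sided 95% confidence interval" (17.7). Control suppression 57% (17.7). Pilot missingness in the target group 6/36 = 17%, arms pooled, with fewer expected here (9.2.3.3). Follow-up viral loads at weeks 12 and 24 only (9.2.3.3).

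**Assumed.** Missingness by arm, which the documents do not give, and the suppression rate among missing participants. Both are varied below.

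**Reproducing the sample size.** With true ratio 1, n per arm = 2[(1 − p)/p](1.96 + 0.842)²/(ln 0.75)². At p = 0.57 this gives 143.1, so 144 per arm and 288 in total. Dividing by 0.83 for 17% missing gives 347, close to 350; power at 350 with 17% missing is 80.6%. The plan's bootstrap cannot be rerun, because its data table is not in the available text, but the scale agrees.

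**Case 1: unequal missingness, common mechanism.** Let m be the proportion missing in an arm, and let missing participants be suppressed at f times that arm's observed rate. The recoded rate is p(1 − m)/(1 − m + f·m). At f = 1 this is p(1 − m), so

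recoded RR = true RR × (1 − m_XR)/(1 − m_TAU).

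With 10% and 20% missing: 0.75 × 0.90/0.80 = 0.844.

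The table gives the probability that the lower Wald limit exceeds 0.75, by exact binomial enumeration at 175 per arm with true rates 0.57 and 0.4275 (true RR 0.75).

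| Missing XR-NTX / TAU | f = 1 | f = 0.5 | f = 0 |
|---|---|---|---|
| 17% / 17% | 2.6% | 2.6% | 2.7% |
| 12% / 17% | 7.0% | 4.7% | 2.7% |
| 10% / 20% | 15.6% | 8.1% | 2.7% |
| 20% / 10% | 0.2% | 0.7% | 2.7% |

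With no missing data the same calculation gives 2.7%, so that is the benchmark.

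**What the planned path does here.** In the 10%/20%, f = 1 case the MAR end returns false non-inferiority to 2.6%. For a trial with observed rates 0.57 and 0.50, the recode gives (0.50 × 0.90)/(0.57 × 0.80) = 0.987 and MAR gives 0.50/0.57 = 0.877. The path does move against non-inferiority.

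**Case 2: equal missingness, mechanism differing by arm.** Take 17% missing in each arm, missing TAU suppressed at the TAU observed rate (0.57) and missing XR-NTX all unsuppressed. For a true XR-NTX rate of 0.4275, the observed rate is 0.4275/0.83 = 0.515.

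- Recode: (0.515 × 0.83)/(0.57 × 0.83) = 0.904; false non-inferiority 35%.
- MAR, 145 observed per arm: 0.515/0.57 = 0.904; false non-inferiority 41%.
- Grid corner matching this mechanism: (0.515 × 0.83)/0.57 = 0.75, the true value.

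With equal missingness, a shift common to both arms leaves the ratio unchanged all along the path. For observed rates 0.57 and 0.50 it stays at 0.877. The arm-specific corner gives (0.50 × 0.83)/0.57 = 0.728. The extreme corner, with all missing TAU suppressed, gives 0.415/(0.57 × 0.83 + 0.17) = 0.645.

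**The flanking exception.** Everyone enters above 200 copies/ml (7.1). A missing week-12 value therefore has an unsuppressed value before it, and a missing week-24 value has no scheduled value after it. Unless chart-abstracted viral loads count as flanking values, which the plan does not say, the exception protects no scheduled value.

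**Limit of the check.** It uses a single-time-point ratio in place of the planned GEE contrast at month 6, without site or alcohol terms.

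**The case against.** A reader might infer that the planned sensitivity analysis never looks in the adverse direction. The documents do not support that. Where TAU simply misses more, the move toward MAR in 17.2 lowers the ratio and removes the bias if MAR is true. Nor do they say that both arms must be shifted together: 17.10 refers to sensitivity analyses in the plural, with the method left open. The gap is that the only stated path ends at MAR and no variation by arm is specified.

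A reader might also infer that TAU will lose more participants. The evidence is weak and points both ways. The injections at weeks 4 to 20 fall on visits that both arms attend, both arms have the week-12 and week-24 draws, and the medical-management passage concerns counselling. Against the extra XR-NTX contacts stands the pilot, where only 5 of 12 (42%) participants with opioid use disorder assigned to XR-NTX started within four weeks. If XR-NTX misses more, the test becomes strict.

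The plan's own premise, that missing participants are mostly unsuppressed, also limits the size. If it holds fully, there is no inflation at any split in Case 1. No document supports a gap as large as ten points, and missingness is expected to fall below the pilot's 17%. The DSMB considers missing data before recommending early termination (17.11), and availability of the primary outcome is reported daily (24.6), though neither is stated to be by arm.

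All of this stands, and it makes the concern conditional. It does not close the gap. Missing need not mean unsuppressed: section 7.4, for example, rules out blood draws during incarceration whatever the participant's viral status. An unknown direction is a reason to fix the analysis in advance.

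**Conclusion.** The concern holds in a limited form. A common recode to unsuppressed is not reliably conservative for non-inferiority on the risk-ratio scale. At a true ratio of 0.75 with TAU at 57%, assumed missingness of 10% on XR-NTX and 20% on TAU raises false non-inferiority from 2.7% to about 16% if missing participants are suppressed at the observed rate, and to about 8% at half that rate. It stays at 2.7% if none are suppressed. The inflation needs both excess TAU missingness and some suppression among the missing.

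The planned move toward MAR handles that case when MAR holds. As stated, it would not expose a mechanism that differs by arm. With 17% missing in each arm, the recode and the MAR analysis can agree on 0.90 when the truth is 0.75, with false non-inferiority of 35% and 41%. The documents give no evidence that this mechanism will occur, so those figures show what the check could miss and are not a forecast. This is a worthwhile improvement to the sensitivity analysis; it does not undermine the primary analysis.

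**What to change.** Keep the recode as the primary analysis. In 17.10:

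- Extend the sensitivity analysis to a two-way tipping-point grid, with separate imputed suppression probabilities for missing XR-NTX and missing TAU values. Include the corner where missing XR-NTX values are unsuppressed and missing TAU values take the TAU observed rate.
- Report week-12 and week-24 missingness by arm.
- State that the non-inferiority conclusion is called robust only if the tipping point is clinically implausible.

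Settle this before outcome data are examined by arm. It takes a little more analysis work and some SAP wording, with no new data and no change in sample size. The downside is that a positive result may have to be reported as sensitive to missing data.
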